8 PHARMACODYNAMICS

Pharmacodynamic samples will be collected for all participants as outlined in Pharmacodynamic sampling [Table 9](#). Samples will be collected at sites with appropriate capabilities. PD samples will not be required from adolescents if the site has policies limiting the daily volume of blood allowed to be drawn as part of a clinical trial (less than the FDA guidelines).

Detailed instructions for sample collection and preparation will be provided in the Laboratory Manual.

Changes in the relevant biomarkers after belumosudil administration will be explored.

Additional samples will be collected from participants enrolled in the site-specific Companion Study for PD analyses as described in [Section 21.13 Appendix M](#).

9 SAFETY

9.1 SAFETY PARAMETERS

The CTCAE v5.0 will be used for grading toxicities. Laboratory results also will be classified using the CTCAE v5.0. Participants will be monitored throughout the treatment and follow-up period for occurrence of AEs (acute, delayed, and/or cumulative), as well as for changes in clinical status, vital sign measurements, and laboratory data. Safety parameters to be measured/assessed include vital sign measurements, PE findings, hematology, clinical chemistry, and ECG recordings. Adverse events will be recorded after the ICF/assent form is signed until 28 days after the last dose of belumosudil.

9.2 ADVERSE EVENT DEFINITION

AE definition

- An AE is any untoward medical occurrence in a clinical study participant, temporally associated with the use of study intervention, whether or not considered related to the study intervention.
- NOTE: An AE can therefore be any unfavorable and unintended sign (including an abnormal laboratory finding), symptom, or disease (new or exacerbated) temporally associated with the use of study intervention.

Definition of unsolicited and solicited AE

- An unsolicited AE is an AE that was not solicited using a participant diary and that is communicated by a participant/participant's parent(s)/legally authorized representative (LAR)(s) who has signed the informed consent. Unsolicited AEs include serious and nonserious AEs.
- Potential unsolicited AEs may be medically attended (ie, symptoms or illnesses requiring a hospitalization, emergency room visit, or visit to/by a health care provider). The participants/ participant's parent(s)/LAR(s) will be instructed to contact the site as soon as possible to report medically attended event(s), as well as any events that, though not medically attended, are of participant/participant's parent(s)/LAR(s) concern. Detailed information about reported unsolicited AEs will be collected by qualified site personnel and documented in the participant's records.
- Unsolicited AEs that are not medically attended nor perceived as a concern by the participant/participant's parent(s)/LAR(s) will be collected during an interview with the participants/participant's parent(s)/LAR(s) and by review of available medical records at the next visit.
- Solicited AEs are predefined local and systemic events for which the participant is specifically questioned, and which are noted by the participants in their diary.

Events meeting the AE definition

- Any abnormal laboratory test results (hematology, clinical chemistry, or urinalysis) or other safety assessments (eg, ECG, radiological scans, vital signs measurements), including those that worsen from baseline, considered clinically significant in the medical and scientific judgment of the Investigator (ie, not related to progression of underlying disease, or more severe than expected for the participant's condition), eg:
 - Leading to belumosudil discontinuation or modification of dosing, and/or,
 - Fulfilling a seriousness criterion, and/or,
 - Defined as an AESI.
- Exacerbation of a chronic or intermittent pre-existing condition including either an increase in frequency and/or severity of the condition.
- New condition detected or diagnosed after study intervention administration even though it may have been present before the start of the study.
- Signs, symptoms, or the clinical sequelae of a suspected drug-drug interaction.
- Signs, symptoms, or the clinical sequelae of a suspected overdose of either study intervention or a concomitant medication.
- Signs, symptoms, or the clinical sequelae of any medication errors, misuse and abuse with belumosudil
- Lack of efficacy or failure of expected pharmacological action per se will not be reported as an AE or SAE. Such instances will be captured in the efficacy assessments. However, the signs, symptoms, and/or clinical sequelae resulting from lack of efficacy will be reported as AE or SAE if they fulfill the definition of an AE or SAE.

Events NOT meeting the AE definition

- Any abnormal laboratory findings or other abnormal safety assessments that are associated with the underlying disease, unless judged by the Investigator to be more severe than expected for the participant's condition.
- The disease/disorder being studied or expected progression, signs, or symptoms of the disease/disorder being studied, unless more severe than expected for the participant's condition.
- Medical or surgical procedure (eg, endoscopy, appendectomy): the condition that leads to the procedure is the AE.
- Situations in which an untoward medical occurrence did not occur (social and/or convenience admission to a hospital).
- Anticipated day-to-day fluctuations of pre-existing disease(s) or condition(s) present or detected at the start of the study that do not worsen.

9.3 EVALUATING ADVERSE EVENTS

The Investigator will determine the seriousness, severity, and causality of AEs based on the definitions that follow.

9.3.1 Serious Adverse Events

An SAE is defined as any untoward medical occurrence that, at any dose, meets one or more of the criteria listed:

a) Results in death

b) Is life-threatening

The term *life-threatening* in the definition of *serious* refers to an event in which the participant was at risk of death at the time of the event. It does not refer to an event, which hypothetically might have caused death, if it were more severe.

c) Requires inpatient hospitalization or prolongation of existing hospitalization

- In general, hospitalization signifies that the participant has been admitted (usually involving at least an overnight stay) at the hospital or emergency ward for observation and/or treatment that would not have been appropriate in the physician's office or outpatient setting. Complications that occur during hospitalization are AEs. If a complication prolongs hospitalization or fulfills any other serious criteria, the event is serious. When in doubt as to whether hospitalization occurred or was necessary, the AE should be considered serious.
- Hospitalization for elective treatment of a pre-existing condition that did not worsen from baseline is not considered an AE.

d) Results in persistent or significant disability/incapacity

- The term disability means a substantial disruption of a person's ability to conduct normal life functions.
- This definition is not intended to include experiences of relatively minor medical significance such as uncomplicated headache, nausea, vomiting, diarrhea, influenza, and accidental trauma (eg, sprained ankle) that may interfere with or prevent everyday life functions but do not constitute a substantial disruption.

e) Is a congenital anomaly/birth defect

f) Other situations:

- Medical or scientific judgment should be exercised by the Investigator in deciding whether SAE reporting is appropriate in other situations such as important medical events that may not be immediately life-threatening or result in death or hospitalization but may jeopardize the participant or may require medical or surgical intervention to prevent one of the other outcomes listed in the above definition. These events should usually be considered serious.

- The following list of medically important events is intended to serve as a guideline for determining which condition has to be considered as a medically important event. The list is not intended to be exhaustive:
 - Intensive treatment in an emergency room or at home for:
 - Allergic bronchospasm.
 - Blood dyscrasias (ie, agranulocytosis, aplastic anemia, bone marrow aplasia, myelodysplasia, pancytopenia, etc).
 - Convulsions (seizures, epilepsy, epileptic fit, absence, etc).
 - Development of drug dependence or drug abuse.
 - ALT $>3 \times$ ULN + total bilirubin $>2 \times$ ULN or asymptomatic ALT increase $>10 \times$ ULN.
 - Suicide attempt or any event suggestive of suicidality.
 - Syncope, loss of consciousness (except if documented as a consequence of blood sampling).
 - Bullous cutaneous eruptions.

9.3.2 Recording and follow-up of AE and/or SAE

AE and SAE recording

- When an AE/SAE occurs, it is the responsibility of the Investigator to review all documentation (eg, hospital progress notes, laboratory reports, and diagnostics reports) related to the event.
- The Investigator will then record all relevant AE/SAE information.
- It is not acceptable for the Investigator to send photocopies of the participant's medical records to the Sponsor's representative in lieu of completion of the required form.
- There may be instances when copies of medical records for certain cases are requested by the Sponsor's representative. In this case, all participant identifiers, with the exception of the participant number, will be redacted on the copies of the medical records before submission to the Sponsor's representative.
- The Investigator will attempt to establish a diagnosis of the event based on signs, symptoms, and/or other clinical information. Whenever possible, the diagnosis (not the individual signs/symptoms) will be documented as the AE/SAE.

Assessment of severity

The Investigator will make an assessment of severity for each AE and SAE reported during the study and assign it to one of the following categories as per NCI CTCAE V5.0 definitions:

- Grade 1 Mild: Asymptomatic or mild symptoms; clinical or diagnostic observations only; intervention not indicated.

- Grade 2 Moderate: Minimal, local or noninvasive intervention indicated; limiting age-appropriate instrumental Activities of Daily Living (ADL). Instrumental ADL refers to preparing meals, shopping for groceries or clothes, using the telephone, managing money, etc.
- Grade 3 Severe: Severe or medically significant but not immediately life-threatening; hospitalization or prolongation of hospitalization indicated; disabling, limiting self-care ADL. Self-care ADL refers to bathing, dressing and undressing, feeding self, using the toilet, taking medications, and not bedridden.
- Grade 4 Life-threatening consequences; urgent intervention indicated.
- Grade 5 Death related to AE.

An event is defined as serious when it meets at least 1 of the predefined outcomes as described in the definition of an SAE, NOT when it is rated as severe.

Assessment of causality

- The Investigator is obligated to assess the relationship between study intervention and each occurrence of each AE/SAE. The Investigator will use clinical judgment to determine the relationship.
- A reasonable possibility of a relationship conveys that there are facts, evidence, and/or arguments to suggest a causal relationship, rather than that a relationship cannot be ruled out.
- Alternative causes, such as underlying disease(s), cGVHD, concomitant therapy, and other risk factors, as well as the temporal relationship of the event to study intervention administration will be considered and investigated.
- For causality assessment, the Investigator will also consult the IB and/or product information, for marketed products.
- The Investigator must review and provide an assessment of causality for each AE/SAE and document this in the medical notes. There may be situations in which an SAE has occurred, and the Investigator has minimal information to include in the initial report to the Sponsor's representative. However, it is very important that the Investigator always make an assessment of causality for every event before the initial transmission of the SAE data to the Sponsor's representative.
- The Investigator may change his/her opinion of causality in light of follow-up information and send an SAE follow-up report with the updated causality assessment.
- The causality assessment is one of the criteria used when determining regulatory reporting requirements.

Follow-up of AEs and SAEs

- The Investigator is obligated to perform or arrange for the conduct of supplemental measurements and/or evaluations as medically indicated or as requested by the Sponsor's representative to elucidate the nature and/or causality of the AE or SAE as fully as possible. This may include additional laboratory tests or investigations, histopathological examinations, or consultation with other health care professionals.
- New or updated information will be recorded in the originally submitted documents.
- The Investigator will submit any updated SAE data to the Sponsor within 24 hours of receipt of the information.

9.3.2.1 Time period and frequency for collecting AE and SAE information

All AEs (serious or nonserious) will be collected from the signing of the informed consent form (ICF) and for 28 days after the last dose of belumosudil at the timepoints specified in the SoA ([Section 21.1](#)), and any SAEs and study drug related nonserious AEs that occur more than 28 days after the last dose of belumosudil.

All SAEs and AESI will be recorded and reported to the Sponsor or designee immediately and under no circumstance should this exceed 24 hours. The Investigator will submit any updated SAE data to the Sponsor within 24 hours of it being available.

Investigators are not obligated to actively seek information on AEs or SAEs after conclusion of the study participation. However, if the Investigator learns of any SAE, including a death, at any time after a participant has been discharged from the study, and the Investigator considers the event to be reasonably related to the study intervention or study participation, the Investigator must promptly notify the Sponsor.

9.3.2.2 Method of detecting AEs and SAEs

Care will be taken not to introduce bias when detecting AEs and/or SAEs. Open-ended and nonleading verbal questioning of the participant is the preferred method to inquire about AE occurrences.

9.3.2.3 Follow-up of AEs and SAEs

After the initial AE/AESI/SAE report, the Investigator is required to proactively follow each participant at subsequent visits/contacts. At the pre-specified study end-date, all SAEs will be followed until resolution, stabilization, the event is otherwise explained, or the participant is lost to follow-up (as defined in [Section 4.8.1](#)).

9.3.3 Reporting Requirements for SAEs

9.3.3.1 *Regulatory reporting requirements for SAEs*

- Prompt notification by the Investigator to the Sponsor of an SAE is essential so that legal obligations and ethical responsibilities towards the safety of participants and the safety of a study intervention under clinical investigation are met.
- The Sponsor has a legal responsibility to notify both the local regulatory authority and other regulatory agencies about the safety of a study intervention under clinical investigation. The Sponsor will comply with country-specific regulatory requirements relating to safety reporting to the regulatory authority, Institutional Review Boards (IRB)/Independent Ethics Committees (IEC), and Investigators.
- Serious adverse events that are considered expected will be specified in the reference safety information (IB).
- Investigator safety reports must be prepared for suspected unexpected serious adverse reactions (SUSARs) according to local regulatory requirements and Sponsor policy and forwarded to Investigators as necessary.
- An Investigator who receives an Investigator safety report describing an SAE, SUSAR or any other specific safety information (eg, summary or listing of SAEs) from the Sponsor will review and then file it along with the IB and will notify the IRB/IEC, if appropriate according to local requirements. It is the responsibility of the Sponsor to assess whether an event meets the criteria for a SUSAR, and therefore, is expedited to regulatory authorities.

9.3.3.2 *Reporting of SAEs*

SAE reporting to the Sponsor via an electronic data collection tool

- The primary mechanism for reporting an SAE to the Sponsor's representative will be the electronic data collection tool.
- If the electronic system is unavailable, then the site will use the paper SAE data collection tool (see next section) to report the event within 24 hours.
- The site will enter the SAE data into the electronic system as soon as it becomes available.
- After the study is completed at a given site, the electronic data collection tool will be taken offline to prevent the entry of new data or changes to existing data.
- If a site receives a report of a new SAE from a study participant or receives updated data on a previously reported SAE after the electronic data collection tool has been taken offline, then the site can report this information on a paper SAE form or to the Sponsor's representative by telephone.
- Contacts for SAE reporting can be found in Emergency Contact Information.

SAE reporting to the Sponsor via paper data collection tool

- Facsimile transmission of the SAE paper data collection tool is the preferred method to transmit this information to the Sponsor's representative.
- In rare circumstances and in the absence of facsimile equipment, notification by telephone is acceptable with a copy of the SAE data collection tool sent by overnight mail or courier service.
- Initial notification via telephone does not replace the need for the Investigator to complete and sign the SAE data collection tool within the designated reporting timeframes.
- Contacts for SAE reporting can be found in Emergency Contact Information.

9.3.3.3 *Pregnancy*

- Details of all pregnancies in female participants and female partners of male participants will be collected after the start of study intervention and until determination of the outcome of the pregnancy.
- If a pregnancy is reported, the Investigator will record pregnancy information on the appropriate form and submit it to the Sponsor within 24 hours of learning of the female participant or female partner of male participant (after obtaining the necessary signed informed consent from the female partner) pregnancy.
- Abnormal pregnancy outcomes (eg, spontaneous abortion, fetal death, stillbirth, congenital anomalies, ectopic pregnancy) are considered SAEs and will be reported as such.
- The participant/pregnant female partner will be followed to determine the outcome of the pregnancy. The Investigator will collect follow-up information on the participant/pregnant female partner and the neonate and the information will be forwarded to the Sponsor. Beyond the estimated delivery date follow-up should last up to 8 weeks.
- Any post-study pregnancy-related SAE considered reasonably related to the study intervention by the Investigator will be reported to the Sponsor as described in [Section 9.3.3](#). While the Investigator is not obligated to actively seek this information in former study participants/pregnant female partner, he or she may learn of an SAE through spontaneous reporting.
- Any female participant who becomes pregnant while participating in the study will discontinue study intervention.

9.4 OTHER SAFETY CONSIDERATIONS

9.4.1 Laboratory Data

All laboratory data obtained during the course of the study should be reviewed. Any abnormal value that leads to a change in participant management (eg, dose reduction or delay, requirement for additional medication or monitoring) or is considered to be of clinical significance by the Investigator should be reported as an AE and/or SAE as appropriate, unless this value is consistent with the participant's present disease state or is consistent with values obtained before entry into the study.

Laboratory results will be classified using the CTCAE v5.0.

10 STUDY STOPPING RULES

In the event of any of the following safety findings occurring in either treatment arm, after at least 10 participants have been enrolled into the mITT population ([Section 11.2.1](#)) in that arm, enrollment will be paused for assessment of safety:

1. Secondary graft failure in >10% of participants.
2. Histological recurrence of underlying malignancy within 6 months of randomization in >20% of participants.
3. Withdrawal due to related AEs in >20% of participants.

Note: The rates of these events observed in the ongoing KD025-208 study as of 7-Mar-2018, with 51 participants enrolled, were 0%, 4% and 4% respectively.

These stopping criteria will be assessed on an on-going basis by the Medical Monitor and shared with the study Steering Committee ([Section 3.2](#)).

The Sponsor has the right to terminate or to stop the study at any time ([Section 16](#)).

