3 INVESTIGATIONAL PLAN

3.1 STUDY DESIGN

This is a Phase 2, randomized, multi-center, open-label, study designed to evaluate the efficacy and safety of belumosudil in participants with active cGVHD after at least 2 prior lines of systemic therapy. The study design is illustrated in [Figure 1](#).

Figure 1 - KD025-213 Study Schema

Participants who consented and/or provided assent documented with a signed an IRB/IEC-approved informed consent/assent form as applicable, and meet all of the eligibility criteria will be enrolled. The study population will be adults and adolescents who:

- Have undergone allogeneic hematopoietic cell transplantation (HCT).
- Have previously received at least 2 lines of systemic therapy for cGVHD.
- Have persistent cGVHD manifestations and systemic therapy for cGVHD is indicated.

A target of $\geq 10\%$ of the enrolled population will have previously received ibrutinib as a therapy for cGVHD.

After confirmation of eligibility during a 14-day screening period, eligible participants will be randomized (1:1) to one of two treatment arms:

- Arm A: belumosudil 200 mg QD
- Arm B: belumosudil 200 mg BID

These doses are selected based upon the data from study KD025-208 ([Section 1.4.1](#)).

Randomization will be stratified according to prior cGVHD treatment with ibrutinib (Yes / No) and severe cGVHD (Yes / No).

With amendment 4, eligible adolescent participants were enrolled into the study at the belumosudil 200 mg QD dose. Since amendment 4, there are no more randomization and stratification factors applied for this group. The additional 20 adults in the companion study will be randomized (1:1) to Arm A or Arm B. The expected sample size in each Arm is therefore: Arm A, N = 93 with addition of 20 adolescents and 10 adults and Arm B, N = 73 with addition of 10 adults. Any adolescent taking a PPI or a strong CYP3A4 inducer will begin C1D1 at the following escalated dose: belumosudil 200 mg BID.

Concomitant treatment with standard of care systemic cGVHD therapies such as calcineurin inhibitors (tacrolimus, cyclosporine), sirolimus, MMF, methotrexate, rituximab or extracorporeal photopheresis (ECP), are permitted as long as the participant has been on a stable dose / regimen of these per the eligibility criteria. Initiation of new systemic cGVHD therapy while on study is not permitted.

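### Section 10 monitors safety by whole arm only, so a high related-AE withdrawal rate among adolescents is unlikely to trigger a pause, and adolescents who were not randomized may not be covered at all

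*Protocol*

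**What the plan says.** Protocol Section 10 sets three triggers: secondary graft failure above 10%, histological recurrence of the malignancy within 6 months of randomization above 20%, and "Withdrawal due to related AEs in >20% of participants". Their scope is set by the opening words: "In the event of any of the following safety findings occurring in either treatment arm, after at least 10 participants have been enrolled". That minimum is counted within each arm's mITT population. The consequence is that "enrollment will be paused for assessment of safety". For context the section cites rates from the earlier KD025-208 study, which, "with 51 participants enrolled, were 0%, 4% and 4% respectively". No age group has its own denominator.

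Section 3.1 and the Synopsis give the expected arm sizes: "Arm A, N = 93 with addition of 20 adolescents and 10 adults", and 73 in Arm B. They add that adolescents enrolled since Amendment 4 receive 200 mg QD without randomization or stratification. Section 3.1 also says: "Any adolescent taking a PPI or a strong CYP3A4 inducer will begin C1D1 at the following escalated dose: belumosudil 200 mg BID". Section 11.3 restricts the mITT population to participants who were randomized and took at least one dose.

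SAP Section 3.11 still limits the third rule to withdrawals within 3 months of randomization. The protocol's rule has no time limit.

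**The concern.** A percentage of the whole arm is a weak detector for a small group that joins a large arm late. If the participants already treated stay in the denominator, many adolescents could withdraw for drug-related toxicity while the arm figure stays under 20%. The study could then report that no stopping criterion was met.

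A second problem comes before that one. Section 10 counts its minimum of 10 in the mITT population, and mITT requires randomization. Adolescents enrolled since Amendment 4 were not randomized, so the text leaves open whether they count. Rule 2 measures 6 months from randomization, a date they do not have.

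At stake is whether the plan's pre-specified safety trigger works for the adolescents.

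**Working it through.** **Inputs**
- Arm A expected size: 93 (Protocol Synopsis and Section 3.1).
- Original size per arm: 63 (Section 11.2).
- Thresholds: strictly more than 10% or 20%; minimum 10 participants (Section 10).
- Background rates: 0%, 4% and 4% among 51 participants (Section 10).

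**Reproducing the plan's figures.** 63 + 10 + 20 = 93 in Arm A and 63 + 10 = 73 in Arm B, total 166, as stated. Arm A without the 20 adolescents is 93 − 20 = 73. The background of 4% is consistent with 2/51 = 3.9%.

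**Reading 1: adolescents count in Arm A.** Assume that the 73 others enroll first and stay in a cumulative denominator. The events needed are the smallest whole number k with k/N > 0.20.
- N = 73 + 10 = 83: 0.20 × 83 = 16.6, so k = 17.
- N = 93: 0.20 × 93 = 18.6, so k = 19.

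Now let all of the first 10 adolescents withdraw for related AEs:
- none of the other 73: 10/83 = 12.0%, no trigger;
- 3 of 73 (73 × 0.04 = 2.9): 13/83 = 15.7%, no trigger;
- 6 of 73 (8.2%): 16/83 = 19.3%, no trigger;
- 7 of 73 (9.6%): 17/83 = 20.5%, the rule fires.

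The documents do not give this study's own withdrawal count, so the background rate has to be shown as a range. The probability that at least 7 of 73 withdraw is 2.7%, 15%, 37% and 60% at true rates of 4%, 6%, 8% and 10%.

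With all 20 adolescents enrolled and 3 background withdrawals, 19 − 3 = 16 of 20 adolescents must withdraw.

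For a true adolescent rate of 50% (an assumed scenario), the pooled rule at N = 93 fires with probability P[Bin(73, p) + Bin(20, 0.5) ≥ 19]:

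| Background rate p among the other 73 | Pooled rule fires |
|---|---|
| 4% | 2.5% |
| 6% | 9% |
| 8% | 20% |
| 10% | 35% |

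Within the 20 adolescents alone, more than 20% means at least 5, and P[Bin(20, 0.5) ≥ 5] = 99.4%.

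If only the original 63 preceded the adolescents, 10 adolescent withdrawals give 10/73 = 13.7%. The rule then needs 15, so 5 of the 63 others (7.9%) would be enough to fire it.

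The graft-failure rule behaves in the same way. More than 10% means 9 events at N = 83 and 10 at N = 93. With the 0% background, that is 9 of the first 10 adolescents or 10 of 20.

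**Reading 2: the mITT definition governs.** Section 10 refers to mITT, Section 11.3 limits mITT to randomized participants, and Section 3.1 ends randomization for adolescents with Amendment 4. Taken together, these participants are neither clearly in the denominator nor clearly counted as events.

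**Cost of a within-adolescent check.** More than 20% is 3 of 10 or 5 of 20. A single look at a true 4% rate gives a false pause with probability 0.6% at 10 adolescents and 0.1% at 20. Section 10 is assessed on an ongoing basis, however, so single looks understate the cost. Checked after every adolescent from 10 to 20, the probability for each 20% rule is about 1.8% at a true 4% rate, 11% at 8% and 18% at 10%.

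**The case against.** The best reply is that the trigger is not the only safeguard. Section 5.10 has toxicity rules for individual participants, and SAEs are reported within 24 hours. The Medical Monitor assesses the criteria continuously and shares them with the Steering Committee, and the Sponsor may stop the study at any time. The drug has also had FDA approval from age 12 since July 2021. All of this is true, and the point should not be read as saying that adolescents go unmonitored. But those arrangements are individual or discretionary; they do not make the pre-specified group trigger sensitive.

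A reader might infer more than the documents support:

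- **That the rule could not fire for adolescents.** It can. Seven withdrawals among the other 73 are enough alongside 10 adolescents, and 16 of 20 adolescents are enough at the 4% background. That background comes from KD025-208, whose participants had no more than 3 prior lines; this trial allows up to 5, so a higher rate is plausible.
- **That the rules were written for adults only.** The amendment history shows that Amendment 1 both lowered the entry age to 12 and revised Section 10.
- **That all adolescents have counted in Arm A since Amendment 2.** Amendment 2 raised both arms to 83, a figure that Section 4.1 still carries. Only Amendment 4 ended randomization, and only for the remaining adolescents, so some may have been randomized to Arm B earlier.
- **That the other 73 are all adults.** Entry age is 12 or older, so the first 63 need not be.
- **That adolescents are the only group still enrolling.** Section 3.1 still describes companion-study adults as to be randomized.

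**Conclusion.** The point holds, with conditions. Neither reading gives adolescents a working trigger. Counted in Arm A, their events are heavily diluted: the third rule stays silent after 10 of 10 adolescent withdrawals unless at least 7 of the other 73 also withdrew. Even at a true adolescent rate of 50%, it fires with a probability of only 3% to 35% over background rates of 4% to 10%. Under mITT, it is unclear that the rules apply to non-randomized adolescents at all.

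The figures rest on an expected Arm A of 93, on the 73 others enrolling first, on a cumulative denominator, and on adolescents who start at BID still counting in Arm A. The documents confirm only the first. The qualitative conclusion does not depend on the 4% background, but the size of the effect does.

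**What to change.** In Section 10:
1. State that adolescents enrolled without randomization are included, and in which denominator.
2. Count time from first dose where there is no randomization date.
3. Add that the same three rates, at the existing thresholds and existing minimum of 10, are also tabulated within the adolescent group. Keep the by-arm rules.
4. Reconcile the third rule with SAP Section 3.11, so that both documents agree on whether a 3-month limit applies.

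The cost is a few sentences and one extra tabulation for the Medical Monitor. The downside is a possible unneeded pause, at the repeated-check probabilities shown in the working. A trigger leads to a pause for assessment and does not by itself end the study.
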